3.7. Other Participant Information

Contraceptive methods used by female participants who are of childbearing potential and heterosexually active (or who become heterosexually active at any time after enrollment), collected on a dedicated eCRF module, will be listed.

4. SAFETY ANALYSIS

Safety and tolerability will be assessed throughout the study, from signing of the Informed Consent Form (ICF) until the participant's last study-related activity. The study will include the following evaluations of safety and tolerability: adverse events, clinical laboratory tests (including TSH, thyroid antibodies, T3, T4, pregnancy tests, Plasma NT pro-BNP), ECG, vital signs, growth (weight, height and BMI), sexual maturation (Tanner Stage), childbearing potential and physical examinations.

Unless otherwise specified, all safety analyses will be carried out descriptively (using the Safety Analysis Set) in the overall population, by age cohort and body weight group.

4.1. Adverse Events

Adverse Events and Treatment-Emergent Adverse Events

- Summaries of below adverse event categories will be summarized according to the study periods *Up-Titration*, *Maintenance after Week 12*, *Maintenance after Week 16* as defined in [Table 2](#).
- All reported adverse events with onset following the start of study treatment, or pre-existing conditions that have worsened since baseline, will be defined as treatment-emergent (TEAE) and will be included in the analysis. TEAEs will be recorded up to EOT + 3 days.
- AEs will be analyzed by period, and the start or worsened date-time of the AEs will be used to determine the period the AE falls in.
- For each TEAE, the percentage of participants who have experienced at least 1 occurrence of the given event will be summarized by system organ class, preferred term, and age cohort.
- TEAEs will be tabulated by severity and relationship and will be summarized by system organ class, preferred term, and age cohort.
- Serious AEs and AEs occurring up to EOT + 3 days that lead to death, hospitalization, treatment discontinuation, dose reduction/interruption will be tabulated and listed.
- AEs that occur during screening and that start prior to first dosing will be included in data listings only.
- All reported adverse event terms will be coded with the latest available MedDRA dictionary version.
- COVID-19 related AEs will be listed.

Adverse Events of Special Interest(AESI):

Adverse events of special interest (AESI) for this study have been defined in [Appendix 2](#).

For each AESI category, the percentage of participants who have experienced at least 1 occurrence of the given event will be summarized by system organ class, dictionary derived preferred term, and age cohort.

AESIs will be also tabulated by severity and will be presented by treatment periods, age cohort, body weight and overall. AESIs will also be summarized by relationship to the study drug.

Number of recurrent AESIs will be counted as the total number of occurrences of any TEAEs, i.e., multiple occurrences for the same preferred term for the same participant will be counted multiple times. Average annualized event rate will be calculated as follows:

- 1) Calculate total number of recurrent TEAEs.
- 2) Calculate participant-years of treatment duration (sum of individual participant time-years in a treatment group)
- 3) Average annualized event rate = (total number of recurrent TEAE) / (subject-years of treatment duration)

The prostacyclin-associated Treatment-Emergent Adverse Events will be summarized by age cohort and body weight group during study period separately.

Deaths

All AEs leading to death occurring up to 3 days after end of treatment, will be listed.

Hospitalization

All hospitalization data from Hospitalization and Adverse Event CRF page will be listed.

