8.1. Appendix 1 List of Abbreviations.....	28
8.2. Appendix 2 Definitions of Adverse Events of Special Interest.....	29

LIST OF IN-TEXT TABLES AND FIGURES

Table 1: SAP Version History Summary 4
Table 2: Study Analysis Set Usage 8
Table 3: Study periods definition..... 8

VERSION HISTORY**Table 1: SAP Version History Summary**

SAP Version	Approval Date	Change	Rationale
Original SAP	10 June 2020	Not Applicable	Initial release
Amendment 1	11 August 2020	See rationale	
 1) Add outputs for COVID-19 related AEs. 2) Add more analysis for concomitant PAH-specific medications 3) Update AESI definitions and provide more details on AESI definitions as an appendix of SAP to align with selexipag program level AESI definitions: ie. Remove thrombocytopenia from anaemia AESI definition, add PVOD AESI and medication error and pregnancy. 4) Add definitions for persistent and recurrent AESIs and average annualized event rates
Amendment 2	02 May 2022	See rationale	
 1) Update the SAP based on Protocol Version 8, Amendment 7 to add optional PK Interim Analysis 3. 2) Add Week 16 CSR deliverable, including all participants having Week 16 assessment. 3) Remove the persistent TEAE definition as the team agree that no separate output is need for it

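### SAP 4.1 defines the recurrent-AESI count and its annualized rate on all TEAEs instead of on the AESI category

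*SAP*

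**What the plan says.** SAP 4.1 first summarizes each AESI category as the percentage of participants with at least one event. It adds: "AESIs will be also tabulated by severity and will be presented by treatment periods, age cohort, body weight and overall". It then turns to repeated events: "Number of recurrent AESIs will be counted as the total number of occurrences of any TEAEs". The explanatory clause attached to that sentence says only that repeats of one preferred term in one participant each count. Three steps follow. Step 1 totals recurrent TEAEs. Step 2 computes "participant-years of treatment duration (sum of individual participant time-years in a treatment group". Step 3 reads "Average annualized event rate = (total number of recurrent TEAE) / (subject-years of treatment duration".

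The SAP version history gives the purpose of this text, introduced in Amendment 1: "Add definitions for persistent and recurrent AESIs and average annualized event rates". Appendix 2 defines 14 AESI categories, each by a list of preferred terms. SAP 3.5 defines treatment duration as first to last intake, inclusive.

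For the wider AE summaries, SAP 4 sets the strata: "in the overall population, by age cohort and body weight group". TEAEs are summarized as the percentage of participants affected, and "TEAEs will be recorded up to EOT + 3 days". SAP 4.1 also splits AEs into up-titration, Week 12 to 16, and maintenance after Week 16. Table 3 in SAP 2.2 leaves the last of these open, up to 5 years after the last participant's first visit. SAP 1.2 says Cohort 3 opened only after the second interim PK analysis of Cohorts 1 and 2. SAP 2.3 says the Week 16 CSR takes all available data once every enrolled participant has finished Week 16 or left the study.

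**The concern.** The quantity named is a recurrent-AESI count; the quantity defined is a count of all TEAEs. Nothing in the count or in steps 1 and 3 refers to Appendix 2. A table programmed from the formula would show the same rate for anaemia, hyperthyroidism and intussusception or ileus within a cohort. It would be dominated by common prostacyclin effects: in the adult GRIPHON study headache affected 65% and diarrhea 42% of selexipag patients (Protocol 1.2.3.4.2), while hyperthyroidism was seen in 1% (Protocol 5.1.10). Safety is the study's secondary objective, and several Appendix 2 categories are rare events for which a correct rate is the useful number.

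There is a second, lesser issue. Outside the AESI rate the SAP has no exposure-adjusted summary of adverse events. In tables that run beyond Week 16, the earlier cohorts have had longer to accumulate events, so crude percentages side by side by age cohort can differ when the underlying risk is equal.

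**Working it through.** The documents give no figure on this point to reproduce. The check is a reading of the text, with two illustrations.

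**Numerator.**
- The count names any TEAE; steps 1 and 3 both name recurrent TEAEs. One wording is used three times, and no sentence restricts it.
- Against this stand the AESI heading, the per-category percentage summary just above, and the Amendment 1 entry, all of which refer to AESIs.
- Intent and formula therefore conflict, and the formula is what would be programmed.

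Illustration, with assumed counts: rate = events / participant-years.
- Literal numerator: 200 TEAEs / 40 participant-years = 5.0 per participant-year.
- Category numerator: 4 events / 40 participant-years = 0.10 per participant-year.
- Ratio: 200 / 4 = 50. With 400 TEAEs and 20 category events it is 400 / 20 = 20.

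The ratio is simply all TEAEs divided by category events. The participant-years cancel, and the documents supply neither count.

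**Denominator.**
- For a whole-treatment rate, first-to-last-intake duration is usable. TEAEs run 3 days past the last dose, but the mismatch is small: 3 / 112 days = 2.7% for 16 weeks of treatment.
- The phrase about a treatment group has no clear referent in a single-arm study. The strata elsewhere in SAP 4 are overall, age cohort and body weight group.
- The rate steps name no study period. The sentence on presentation by treatment period is about the AESI severity tabulation.

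**Follow-up.**
- The up-titration and Week 12 to 16 windows have the same planned length in every cohort, so they compare fairly.
- Maintenance after Week 16, and any summary running to EOT + 3 days, does not.

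Illustration: P(at least one event) = 1 − exp(−rate × time), with the same assumed constant rate for two children. One has 16 weeks of follow-up (112 / 365.25 = 0.307 years). The other has 2.14 years, the gap from the interim 2 report (12 March 2020, Protocol 13) to SAP Amendment 2 (2 May 2022). That gap stands in for a Week 16 CSR cut-off that the documents do not give.

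| Assumed rate per year | 16 weeks | 2.14 years |
|---|---|---|
| 0.1 | 3.0% | 19.3% |
| 0.25 | 7.4% | 41.4% |
| 0.5 | 14.2% | 65.7% |
| 1.0 | 26.4% | 88.2% |

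These are individual contrasts, not predicted cohort differences. Cohort averages would lie closer together, because entry is staggered and some children stop treatment.

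**The case against.** The best reply is that no programmer would implement a rule giving 14 categories the same number. The sentence sits under the AESI heading, and its explanatory clause shows that its job is to say repeats are counted. That makes the intended meaning clear and the cause a slip. It does not remove the need for the fix: a prespecified formula should be right as written, and this one is not.

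A reader might also infer that the denominator is defective because a by-period rate would have no matching time. The documents do not support this. No sentence requires the annualized rate by period, and if one were wanted, the start and end dates in Table 3 would supply the time. Only the treatment-group wording needs repair.

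On follow-up, the objection is stronger. The safety analyses are descriptive, no formal comparison of age cohorts is planned, the first two periods are comparable, and SAP 3.5 lists each participant's exposure duration, so the imbalance can be seen. A reader might try to put a size on it from adult data. GRIPHON's 43.8% with an SAE and 31.7% with an AE leading to discontinuation, over a mean 1.5 years, imply −ln(1 − 0.438) / 1.5 = 0.384 and −ln(1 − 0.317) / 1.5 = 0.254 per year. Treated as competing constant hazards, these return 0.384 / 0.638 × (1 − exp(−0.638 × 1.5)) = 37% with an SAE at 1.5 years, not 43.8%. The model misses its own calibration point, and cohort entry dates and the report cut-off are also not given. Modelled cohort percentages from it are not evidence about this trial. What stands is the direction of the effect, not its size.

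**Conclusion.** The numerator is wrong as written. Taken literally, SAP 4.1 yields an all-TEAE rate under an AESI label, the same for every category in a stratum. This rests on the text alone and needs no assumption. The size of the error depends on each category's share of all TEAEs; the 20- to 50-fold ratios above are illustrations. It would be going too far to say that the sponsor intends such a rate or that the safety conclusions would be invalid: the surrounding text points to an AESI rate, the percentage summaries by category are unaffected, and no primary analysis, error rate or sample size is involved.

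The follow-up point is a worthwhile addition, not a correction. It applies only to tables extending beyond Week 16, and mainly to the Week 16 CSR. Its direction assumes equal underlying risk and longer follow-up in Cohorts 1 and 2. The Data Presentation Plan, which decides the outputs for each report, was not available.

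**What to change.** **Main change, SAP 4.1.** In the count and in steps 1 and 3, define the numerator as treatment-emergent occurrences whose preferred term belongs to the given Appendix 2 category. In step 2, replace the treatment-group phrase with participant-years in the same stratum: age cohort, body weight group or overall. If the rate is also to be shown by study period, say so and use participant-time within that Table 3 period. SAP 4.1 currently points to Table 2 for the periods; correct that cross-reference at the same time. The cost is one or two lines of text.

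**Optional addition.** In the maintenance-after-Week-16 and whole-treatment tables only, add participants with a first event per 100 participant-years at risk, for TEAEs, SAEs and AEs leading to discontinuation. State where time at risk ends for children still on treatment at the Week 16 CSR, since the SAP gives no end date for them. The cost is a few table columns and a derivation of time at risk. The downside is that these rates assume a roughly constant hazard and will be imprecise with about 20 participants per cohort.

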4.2. Clinical Laboratory Tests

The following laboratory parameters are evaluated:

- Hematology:
 - Hemoglobin (g/L)
 - Hematocrit (L/L)
 - Erythrocyte count ($10^9/L$)
 - Leukocyte count with differential counts ($10^9/L$)
 - Platelet count ($10^9/L$)
- Clinical chemistry:
 - Alanine aminotransferase (U/L)
 - Aspartate aminotransferase (U/L)
 - Alkaline phosphatase (U/L)
 - Total and direct bilirubin ($\mu\text{mol/L}$)
 - Creatinine ($\mu\text{mol/L}$)
 - Creatinine clearance (mL/min)
 - Serum urea nitrogen (mmol/L)
 - Uric acid ($\mu\text{mol/L}$)
 - Glucose (mmol/L)
 - Cholesterol, triglycerides (mmol/L)
 - Sodium, potassium, chloride, calcium (mmol/L)
 - Albumin (g/L)
 - NT-pro BNP (pmol/L)
 - TSH (mU/L)
 - Free T3 and free T4 (pmol/L)
 - Thyroid antibodies (U/mL)

In addition, local laboratory parameters might be available under certain circumstances and recorded in the CRF.

All recorded assessments, whether from central or local laboratory (including unscheduled) will be assigned to the most appropriate visit time points according to the best fitting time-window for that assessment

If data from a local laboratory and from the central laboratory are available for the same date, the central laboratory value will be used; if more than one valid assessment are available on the same timepoint window in the same lab, the mean value will be considered.

A laboratory test abnormality is defined as any value outside the normal range as provided by the laboratory. The direction of the abnormality (below or above the normal range) is indicated using 'H' and 'L', if applicable.

A marked (alert) laboratory test abnormality is defined as any value that fulfills the applicable condition listed in the table below for LL / HH (or LLL / HHH, respectively):

Safety parameter	Marked Abnormally Low Values		Marked Abnormally High Values	
	LL	LLL	HH	HHH
Hematology				
Hemoglobin (g/L)	< 100	< 80	Increase (> 20 g/L) above ULN or above baseline if baseline is above ULN	Increase (> 40 g/L) above ULN or above baseline if baseline is above ULN
Hematocrit (L/L)	< 0.28 F < 0.32 M	< 0.20	> 0.55 F > 0.60 M	> 0.65
Erythrocyte count (10 ⁹ /L)	NA	NA	NA	NA
Leukocyte count with differential counts (10 ⁹ /L)	< 3.0	< 2.0	> 20.0	> 100.0
Platelet count (10 ⁹ /L)	< 75	< 50	> 600	> 999
Clinical chemistry				
AST (U/L)	NA	NA	> 3 ' ULN	> 5 ' ULN
ALT (U/L)	NA	NA	> 3 ' ULN	> 5 ' ULN
Alkaline phosphatase (U/L)	NA	NA	> 2.5 ' ULN	> 5 ' ULN
Total bilirubin (µmol/L)	NA	NA	> 2 ' ULN	> 5 ' ULN
Direct bilirubin (µmol/L)	NA	NA	> 2 ' ULN	> 5 ' ULN
Creatinine (µmol/L)	NA	NA	> 1.5 ' ULN or > 1.5 ' baseline if baseline is above ULN	> 3 ' ULN or > 3 ' baseline if baseline is above ULN
Serum urea nitrogen	NA	NA	> 2.5 x ULN	> 5 x ULN
Glucose (mmol/L)	< 3.0	< 2.2	> 8.9	> 13.9
Sodium (mmol/L)	NA	< 130	> 150	> 155
Potassium (mmol/L)	< 3.2	< 3.0	NA	> 6.0
Calcium (mmol/L)	< 2.0	< 1.75	> 2.9	> 3.1

ALT = alanine aminotransferase; AST = aspartate aminotransferase; F = female; M = male; ULN = upper limit of normal range.

Treatment-emergent marked laboratory abnormalities are defined as all marked laboratory abnormalities with onset after the study treatment start and up to EOT+3 days, that were not present at baseline or worsened during the course of the study. They will be analyzed on the Safety Analysis Set overall, by age cohort and body weight group.

For each category (i.e., LL, LLL, HH, HHH), treatment-emergent marked laboratory abnormalities are summarized for each laboratory variable overall, by age cohort and body weight group, displaying counts and percentages of participants with at least one marked treatment-emergent abnormality. Percentages are calculated by dividing the number of participants with at least one marked abnormality for the parameter under consideration by the number of participants with any post-baseline measurement.

The number of participants with laboratory abnormalities/marked abnormalities (any value outside the normal ranges for the laboratory) will be also tabulated as shift tables against baseline.

Absolute values and changes from baseline will be determined for each parameter and participant at the different timepoints of assessment and summarized overall, by age cohort and body weight group for the Safety Analysis Set. For graphs or tables with mean values, to account for changing reference ranges across age and gender, certain central and local laboratory values (Y_{ori}) and their reference ranges (LLN_{ori} , ULN_{ori}) will be normalized as Y_{norm} using a standard range (LLN , ULN) as follows:

$$Y_{norm} = LLN + \frac{(Y_{ori} - LLN_{ori})}{(ULN_{ori} - LLN_{ori})} \times (ULN - LLN)$$

If the value is negative after normalization, zero will be assigned.

The laboratory tests that require normalization and their standard ranges to be used are:

- TSH: 0.34 - 5.60 (mIU/L)
- Free T3: 4.5 - 7.8 (pmol/L)
- Free T4: 10 - 24 (pmol/L)
- Hemoglobin: 116 - 164 (g/L)
- Hematocrit: 0.34 - 0.48 (L/L)
- Erythrocyte count: 4.1 - 5.6 ($10^{12}/L$)
- Leukocyte count: 3.80 - 10.70 ($10^9/L$)
- Neutrophil count: 1.65 - 8.15 ($10^9/L$)
- Lymphocyte count: 0.95 - 5.25 ($10^9/L$)
- Monocyte count: 0.40 - 0.90 ($10^9/L$)
- Monocyte/leukocyte: 4.0 - 7.0 (%)
- Eosinophil count: 0.00 - 0.20 ($10^9/L$)
- Eosinophil/leukocyte: 0.0 - 4.1 (%)
- Platelet count: 140 - 400 ($10^9/L$)
- Creatinine: 40 - 83 ($\mu\text{mol}/L$)
- Alkaline phosphatase: 31-110 (U/L)

- Alanine aminotransferase: 6-34 (U/L)
- Aspartate aminotransferase: 10-40 (U/L)
- Uric Acid: 137-404 ($\mu\text{mol/L}$)
- Albumin: 33 - 47 (g/L)
- Triglyceride: 0.44 - 1.40 (mmol/L)
- Cholesterol: 3.23 - 5.48 (mmol/L)

All individual laboratory data will be listed and a separate listing for participants with laboratory abnormalities will also be provided, as well as a separate listing of participants with treatment-emergent marked laboratory abnormalities.

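### The SAP's marked-abnormality table puts total leukocyte limits on the differential counts as well, so ordinary lymphocyte and neutrophil values would be counted as marked

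*SAP*

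**What the plan says.** SAP section 4.2 states that "A marked (alert) laboratory test abnormality is defined as any value that fulfills the applicable condition listed in the table below". In that table the only white-cell row is "Leukocyte count with differential counts", in 10^9/L, with LL < 3.0, LLL < 2.0, HH > 20.0 and HHH > 100.0. Neutrophils, lymphocytes, monocytes and eosinophils have no row of their own. The erythrocyte row is NA in all four columns.

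Later in the section the SAP treats the cell types as separate variables with their own standard ranges, used to normalize means. These include "Leukocyte count: 3.80 - 10.70", "Lymphocyte count: 0.95 - 5.25" and "Monocyte count: 0.40 - 0.90". Neutrophils are given as 1.65-8.15 and eosinophils as 0.00-0.20.

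Treatment-emergent marked abnormalities are those arising after treatment start, up to EOT + 3 days, that were absent at baseline or worsened. They are counted by category (LL, LLL, HH, HHH) for each laboratory variable. Marked abnormalities also go into shift tables against baseline. Protocol section 6.2 lists treatment-emergent marked laboratory abnormalities among the safety endpoints.

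**The concern.** Marking applies to any value that meets the row's condition, and the row names the differentials. A programmer who follows the text would therefore test a lymphocyte or monocyte count against limits scaled for the total count. A differential is only a part of the total, so the low limits are too high for it. The high limits are too loose: the largest differential upper limit is 8.15, and twice that (16.3) is still below 20, so real elevations would not be marked.

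The study has one arm. A false flag produced by ordinary variation has no control group to show it as background, and it could be read as an effect of treatment in an endpoint table.

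**Working it through.** The documents give no figure on this point to reproduce. The check compares the SAP's marked limits with its own standard ranges, and then simulates the treatment-emergent count with no drug effect.

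**1. Share of each standard range below the low limits.** Formula: (limit - lower) / (upper - lower), bounded to 0-1.

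- Total leukocytes, 3.80-10.70: both limits lie below 3.80, so 0% and 0%.
- Lymphocytes, 0.95-5.25: (3.0 - 0.95)/4.30 = 47.7% below 3.0; (2.0 - 0.95)/4.30 = 24.4% below 2.0.
- Neutrophils, 1.65-8.15: (3.0 - 1.65)/6.50 = 20.8%; (2.0 - 1.65)/6.50 = 5.4%.
- Monocytes, 0.40-0.90, and eosinophils, 0.00-0.20: 100% below 2.0, so every value in range is LLL.

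**2. Share of values, taking each range as a central 95% interval (assumption).** Log-normal: median = sqrt(lower x upper), log SD = ln(upper/lower)/3.92. Normal: mean = midpoint, SD = (upper - lower)/3.92.

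| Count | Log-normal: median, log SD | < 3.0 / < 2.0 | Normal: mean, SD | < 3.0 / < 2.0 |
|---|---|---|---|---|
| Lymphocytes | 2.23, 0.436 | 75% / 40% | 3.10, 1.10 | 46% / 16% |
| Neutrophils | 3.67, 0.408 | 31% / 7% | 4.90, 1.66 | 13% / 4% |
| Total leukocytes | 6.38, 0.264 | 0.2% / 0.0% | 7.25, 1.76 | 0.8% / 0.1% |

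**3. False treatment-emergent LL or LLL by Week 16.** Protocol Table 4 schedules hematology after baseline at Weeks 4, 12 and 16, so there are three post-baseline tests. A child counts if any of them falls in a worse low category than baseline. The within-child CV of 15-25% is an assumption; the documents give none. The within-child part is sqrt(ln(1 + CV^2)) on the log scale, or CV x mean in the normal model. The between-child variance is what remains of the range's total variance. For total leukocytes at 25% in the normal model nothing remains, and it is set to zero. Each case used 400,000 simulated children.

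| Count | Log-normal, CV 15% to 25% | Normal, CV 15% to 25% |
|---|---|---|
| Lymphocytes | 24% to 36% | 28% to 43% |
| Neutrophils | 19% to 31% | 13% to 22% |
| Total leukocytes | 0.5% to 0.6% | 1.8% to 2.8% |

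**4. Sensitivity.** If the SAP range is taken as between-child variation only (log-normal), the results are 23-32%, 19-29% and 1.1-3.9% in the same order. If the within-child SD in the normal model is scaled to each child's own level, neutrophils fall to about 10-21%. The size moves with the model, but the contrast with the total count remains in each of these variants.

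**The case against.** The strongest reply is that the row label is carried over. The same wording stands in the list of tests in SAP section 4.2 and in Protocol section 7.2.4.2. The erythrocyte row likewise repeats its list label, including a unit (10^9/L) that differs from the 10^12/L used for its standard range. The limits plainly fit the total count, so the sponsor may have meant only that. This is plausible, and it is why the point is about the text as written and not about a known programming rule. It does not settle the matter, because nothing in the SAP restricts the row.

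A second reply is that the standard ranges are targets for normalizing means, and that normality is defined by the laboratory's own ranges. That is correct, so the percentages are illustrative. They use the only ranges the documents give.

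A third is that the harm is limited. Ordinary high/low flags use the laboratory's ranges, and all individual results are listed, so a careful reader could recognise an artefact. That stands and keeps the point small.

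A reader might also infer two stronger claims.

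- **That every child would show a treatment-emergent marked monocyte or eosinophil value.** The documents do not support this. Such values would already be LLL, the worst low category, at baseline and would mostly be removed. They would return only if worsened, which is undefined, were taken to mean any fall. They would still appear in the shift tables.
- **That the hematocrit row has the same fault, because its LL limits ("< 0.28 F < 0.32 M") have no age split.** The only hematocrit range in the documents is 0.34-0.48, and both limits lie below it, so no value in that range is flagged. Over-flagging of young boys would need an age-specific range that the documents do not contain.

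**Conclusion.** The point holds for the leukocyte row as written. Limits that suit only the total count extend to the differentials, and lymphocytes and neutrophils would then cross them through ordinary variation. By Week 16, with no drug effect, the false treatment-emergent rate is roughly 24-43% for lymphocytes and 13-31% for neutrophils, against 0.5-3% for total leukocytes.

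These figures rest on a literal reading of the row, on the SAP's standard ranges taken as 95% intervals, on an assumed within-child CV of 15-25%, and on the choice of distribution. The direction does not depend on the simulation: both ranges straddle both low limits, and the total-count range lies above them.

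Only descriptive safety tables are affected. The primary pharmacokinetic endpoint and the dose-confirmation criteria in Protocol section 3.1 do not use these flags.

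**What to change.** In the SAP section 4.2 table, relabel the row as the total leukocyte count and keep its four limits. Then do one of the following:

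- enter each differential count as NA, as is already done for erythrocytes; or
- give each differential limits relative to the laboratory's own LLN and ULN, as the table already does with ULN for transaminases, bilirubin and creatinine.

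NA is the smaller change. Its price is that a low neutrophil count would appear only among the ordinary high/low abnormalities. Relative limits keep a marked category but need multipliers, which the documents do not supply and the sponsor would have to justify.

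Either way the cost is a line or two of SAP text and a small programming change. No new data are needed, because the laboratory's normal ranges are already in use. For outputs already produced, such as those for the Canada submission in SAP section 2.3, it is enough to check how this row was programmed and correct it if the differentials were included.
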